12.1.1. Screening Assessments

Assessments will be conducted in the following order. Both eyes will be evaluated at all ophthalmic assessments:

- 1. Obtain written informed consent
- 2. Obtain medical history, ocular history, and demographics (can be performed anytime during the visit)
- 3. Evaluate and record patient's medication usage (including concomitant medications taken within the past 30 days) (can be performed anytime during the visit)
- 4. Assess BCVA (ETDRS) with manifest refraction
- 5. Perform pupil measurement
- 6. Perform slit lamp biomicroscopy
- 7. Perform corneal staining
- 8. Measure IOP at 8 a.m.
- 9. Perform gonioscopy
- 10. Perform pachymetry (contact)
- 11. Perform specular microscopy, non-contact (can be performed anytime during the visit beyond the pachymetry exam)
- 12. Assess VF
- 13. Perform anterior chamber OCT
- 14. Perform dilated funduscopic exam
- 15. Perform body system assessment (can be performed anytime during the site visit)
- 16. Assess vital signs (can be performed anytime during the site visit)
- 17. Collect non-fasting blood and urine for clinical laboratory tests (can be performed any time after the 10 a.m. IOP measurements)
- 18. If female of childbearing potential, perform urine pregnancy test
- 19. Verify that patient meets all applicable entry criteria

- 20. Begin washout of patient's current PGA therapy.
 - 21. Query patient about whether or not they have experienced symptoms during the exam procedures suggesting an AE. AEs will be documented.

The patient will be asked to return for the baseline visit after 4 weeks. The washout period may be extended up to two additional weeks if it remains safe for the patient, and to accommodate the patient's or the investigator's schedule.

Before subjects leave the clinic, they should receive an appointment for their next study visit and the following instructions:

- Discontinue use of all eye drop medications until the end of the study (if appropriate). With your doctor's approval, you may be able to use artificial tear eye drops.
- At all visits except Visit 3 and Visit 4, be prepared for a long clinic visit. You will be expected to have IOP measurements at 8:00 a.m., 10:00 a.m., and 4:00 p.m. You may leave the clinic after the 10:00 a.m. assessments with your doctor's approval.
- Call your study site if you have any problems.
- Remember not to wear contact lenses

12.2. Visit 2/Day -7 to -1/Baseline, Cohort 2

Patients will be queried about changes in medications and whether or not they have experienced symptoms suggesting an AE. AEs will be documented.

12.2.1. Baseline Assessments

Assessments will be conducted in the following general order. Both eyes will be evaluated at all ophthalmic assessments:

- 1. Assess BCVA (ETDRS) with manifest refraction
- 2. Perform pupil measurement
- 3. Perform slit lamp biomicroscopy
- 4. Perform corneal staining
- 5. Measure IOP at 8:00 a.m.
 - IOP must be between 22-34 mm Hg in both eyes with a ≤4 mm Hg difference between each eye at 8:00 a.m. (±30 minutes)
 - IOP must increase of at least 4 mmHg in each eye compared to the pre-washout baseline
- 6. Perform gonioscopy
- 7. Perform pachymetry (contact)
- 8. Perform specular microscopy (non-contact) (can be performed anytime during the visit)

- 9. Assess vital signs (can be performed anytime during the site visit)
- 10. Measure IOP at 10:00 a.m. (\pm 30 minutes)
 - IOP must be between 22-34 mm Hg in both eyes with a ≤4 mm Hg difference between each eye at 10:00 a.m. (±30 minutes)
- 11. Collect non-fasting blood and urine for clinical laboratory tests **and** systemic PK (can be performed after the 10 a.m. IOP)
- 12. If female of childbearing potential, perform urine pregnancy test
- 13. Measure IOP at 4:00 p.m. (±30 minutes)
 - IOP must be between 19-30 mm Hg in both eyes with a ≤4 mm Hg difference between each eye at 4:00 p.m. (±30 minutes)
- 14. Perform dilated funduscopic examination
- 15. Verify that patient meets all entry criteria

Patients are expected to remain in the clinic for the completion of all procedures (\sim 7:30 a.m. to \sim 5:00 p.m.). However, at the discretion of the investigator, patients will be permitted to leave the clinic after completing the 10:00 a.m. IOP measurement and will return to the clinic before the 4:00 p.m. IOP measurement. Any patient that leaves the clinic will be instructed to return no later than 30 minutes prior to the 4:00 p.m. IOP measurement.

12.3. Visit 3/Day 1/Dosing/Treatment, Cohort 2

Query patient about changes in medications and whether or not they have experienced symptoms suggesting an AE. AEs will be documented.

12.3.1. Pre-dose Assessments

Assessments will be conducted in the following general order. Both eyes will be evaluated at all ophthalmic assessments:

- 1. Assess BCVA (ETDRS) with manifest refraction
- 2. Perform slit lamp biomicroscopy
- 3. Perform corneal staining
- 4. Measure IOP at between 6:00 a.m. and 10:00 a.m. a.m. (±30 minutes)
- 5. Perform gonioscopy
- 6. Perform pachymetry (contact)
- 7. Perform specular microscopy (non-contact) study eye only
- 8. Instill one drop of VIGAMOX into the study eye
- 9. Verify that patient meets all entry criteria

12.3.2. Study Eye Assignment and Study Drug Administration

Patients will be assessed to ensure they still qualify to participate in the study based on the inclusion/exclusion criteria (Section 11.3 and Section 11.4). The patient's study eye will be assigned to receive 2 ENV515-3 (travoprost) Intracameral Implant(s) into the study eye via intracameral injection administered via the provided intracameral implant applicator. The study-trained investigator will administer the dose of study medication into the study eye between 6:00 a.m. and 10:00 a.m. (±30 minutes). Timolol maleate 0.5% ophthalmic solution will be administered into the non-study eye by the patient at 8 p.m. (±60 minutes) on the day of Visit 3.

12.3.3. Post-dose Assessments

- 1. Perform slit lamp biomicroscopy
- 2. Dispense bottle of timolol maleate 0.5% ophthalmic solution to the patient

Patients are expected to remain in the clinic for the completion of all procedures (\sim 7:30 a.m. to \sim 12:00 p.m.); however, at the discretion of the investigator, patients will be permitted to leave the clinic following the completion of the dosing.

12.3.4. Patient Instructions

Before patients leave the clinic, they should receive an appointment for their next study visit and the following instructions:

- Remember to use timolol maleate 0.5% ophthalmic solution twice daily (as close to 8:00 a.m. and 8:00 p.m. as you can ± 60 minutes) in the non-study eye. DO NOT PUT timolol maleate 0.5% ophthalmic solution in the eye that received the ENV515 implants. Continue using timolol maleate 0.5% ophthalmic solution until one day prior to the last study visit, Visit 16 (Month 12 ± 7 days). Please remember to bring timolol maleate 0.5% ophthalmic solution with you to at each subsequent visit so that it can be administered after the 8:00 a.m. IOP measurement. It will need to be collected from you before issuing a new bottle at applicable visits.
- Continue to withhold (not use) all your other eye drop medications until the end of the study (if appropriate). With your investigator's approval, you may be able to use artificial tear eye drops.
- Remember not to wear contact lenses
- Call your study site if you have any problems
- Please avoid physical activities associated with jarring physical motions, such as horseback riding, for the rest of the study.

12.4. Visit 4/Day 2 + up to 3 Days/Treatment Period, Cohort 2

Query patient about changes in concomitant medications and whether or not they have experienced symptoms suggesting an AE. AEs will be documented.

Assessments will be conducted in the following order. Both eyes will be evaluated at all ophthalmic assessments unless otherwise noted:

- 1. Assess BCVA (ETDRS) with manifest refraction
- 2. Perform slit lamp biomicroscopy
- 3. Perform corneal staining
- 4. Measure IOP at 8:00 a.m. (±30 minutes, please make sure that timolol maleate 0.5% ophthalmic solution is administered after the IOP measurement)
- 5. Perform gonioscopy
- 6. Perform pachymetry (contact)
- 7. Perform specular microscopy (non-contact) study eye only

Patients are expected to remain in the clinic for the completion of all procedures (\sim 7:30 a.m. to \sim 10:00 a.m.). Before patients leave the clinic, they should receive an appointment for their next study visit and the instructions provided in Section 12.3.4.

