Timolol maleate 0.5% distribution and collection ²	X	X	X	X	X	X	X
Exit patient, complete exit form							X

- Specular microscopy is needed for all study eyes on all indicated visits; for non-study eyes, it is collected only during Exit/Early Exit (Visit 22). Additional measurements may be taken at the investigator's discretion.
- Timolol maleate 0.5% ophthalmic solution is given to the patient to continue dosing BID for the remainder of the study. Patients will be instructed to return their used bottle(s) at each visit for accountability purposes. A new supply of timolol maleate 0.5% ophthalmic solution will be provided on a monthly basis through Month 17 (Visit 21). During post dose study visits, ensure timolol maleate 0.5% ophthalmic solution is administered after the 8 AM IOP measurement.
- Always capture the ENV515 implant(s) in the field of view of at least one OCT image.
- V16/Month 12 Time and Events Schedule should only be used if patients are continuing into the Cohort 2 Study Extension 1. If the patients are continuing into the Cohort 2 Study Extension 2, V22/Month 18 should follow the Time and Events Schedule in the Cohort 2 Study Extension 2 Synopsis, Table 4.

ENV515-01 PHASE 2A CLINICAL STUDY, COHORT 2 EXTENSION 2

Cohort 2 Extension 2 Protocol Synopsis

Investigational Product: ENV515-3 (Travoprost) Intracameral Implant

Phase: 2a Cohort 2 Extension 2

Cohort 2 Study Extension 2 Objective:

• Extend the ENV515-01 Ph2a Cohort 2 study duration beyond 18 months (12 month Cohort 2 + 6 month Extension 1) by an additional 3 months in Extension 2 to continue evaluation of the ENV515-3 long term safety, efficacy, and biodissolution in patients with bilateral ocular hypertension or primary open-angle glaucoma

Clinical Hypotheses:

 A single dose of two ENV515-3 (travoprost) Intracameral Implants will demonstrate end of duration of IOP treatment effect and full biodissolution in the time period between 13 and 21 months

Cohort 2 Study Extension 2 Design:

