Gonioscopy	X	X	X	X	X	X	X
Gonioscopy photographs (at selected sites)	X	X	X	X	X	X	X
Pachymetry	X	X	X	X	X	X	X
Specular microscopy	X^2	X^2	X^2	X^2	X^2	X^2	X
Visual field							X
Anterior chamber OCT ³	X	X	X	X	X	X	X
Dilated fundus exam							X
Body System Assessment							X

Version 19Feb2018

Procedure	Treatment V22 Month 18 +/- 7 days ¹	Treatment V23 Month 19 +/- 7 days	Treatment V24 Month 20 +/- 7 days	Treatment V25 Month 21 +/- 7 days	Treatment V26 Month 22 +/- 7 days	Treatment V27 Month 23 +/- 7 days	Exit/Early Exit V28 Month 24 +/- 7 days
Vitals							X
Hematology, chemistry and urinalysis							X
Urine Pregnancy test							X
Timolol maleate 0.5% distribution and collection ⁴	X	X	X	X	X	X	X
Exit patient, complete exit form							X

¹ V22/Month 18 Time and Events Schedule should only be used if patients are continuing into the Cohort 3 Study Extension 2.

Specular microscopy is needed for all study eyes on all indicated visits. Additional measurements may be taken at the investigator's discretion.

Timolol maleate 0.5% ophthalmic solution is given to the patient to continue dosing BID for the remainder of the study. Patients will be instructed to return their used bottle(s) at each visit for accountability purposes. A new supply of timolol maleate 0.5% ophthalmic solution will be provided on a monthly basis through Month 23 (Visit 27). During post dose study visits, ensure timolol maleate 0.5% ophthalmic solution is administered after the 8 AM IOP measurement.

⁴ Capture the ENV515 implant(s) in the field of view of at least one OCT image.

TABLE OF CONTENTS, LIST OF TABLES, AND LIST OF FIGURES TABLE OF CONTENTS

PROTOC	OL APPROVAL SIGNATURE PAGE	2
INVESTI	GATOR PROTOCOL AGREEMENT	3
COHORT	1 PROTOCOL SYNOPSIS	4
COHORT	2 PROTOCOL SYNOPSIS	11
COHORT	2 EXTENSION 1 PROTOCOL SYNOPSIS	19
COHORT	2 EXTENSION 2 PROTOCOL SYNOPSIS	23
COHORT	3 PROTOCOL SYNOPSIS	27
COHORT	3 EXTENSION 1 PROTOCOL SYNOPSIS	35
COHORT	3 EXTENSION 2 PROTOCOL SYNOPSIS	39
TABLE C	OF CONTENTS, LIST OF TABLES, AND LIST OF FIGURES	43
LIST OF	ABBREVIATIONS AND DEFINITIONS OF TERMS	52
1.	INTRODUCTION	54
1.1.	Description of Investigational Product	54
1.2.	Overall Trial Design	56
1.3.	Justification for Route of Administration and Dose Selection	57
1.4.	Summary of Results from Cohort 1 of ENV515-01 Phase 2a Study	60
1.4.1.	Summary of Disposition of Cohort 1 Patients in ENV515-01 Phase 2a Study	60
1.4.2.	Summary of Efficacy Results from Cohort 1 of ENV515-01 Phase 2a Study	61

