On the Day 1 Dosing (Visit 3), low dose of ENV515-3 in Cohort 2, or low or high doses of ENV515-3-2 in Cohort 3 will be administered. Following Day 84 of the treatment phase (Dosing Visit 3/Day 1 to Treatment Visit 7/Day 84 [±7 days]), an analysis of IOP treatment effect as a change in mean diurnal IOP from mean diurnal IOP baseline will be conducted as the primary efficacy outcome measure. Following the completion of the rest of the study treatment period Month 4 (Visit 8) to Exit/Early Exit (Visit 16, Visit 22, or Visit 25) for the Cohort 2 alone, all safety and tolerability analyses will be conducted (Figure 6).

Figure 6: Study Design for ENV515-01 (Cohorts 2 and 3)

For Cohort 2, the study design included up to 26 clinic visits over approximately 23 months (12 months of Cohort 2, 6-month optional Extension 1, and 3-month optional Extension 2). For Cohort 3, the study design includes up to 28 clinic visits over approximately 26 months (12 months of Cohort 3,6-month optional Extension 1, and 6-month optional Extension 2). Following the Screening Visit, patients will be required to washout current glaucoma medication(s) (Section 16.1) for 4 weeks with up to an additional 2-week extension or 6 weeks

97 Version 19Feb2018

Communition

depending on Cohort. Patients will be required to return for an IOP baseline check during the Baseline Visit (Visit 2/Day -7 to -1) following the wash-out period. A single dose of ENV515-3 (two implants/eye) or ENV515-3-2 (one or two implant(s)/eye) will be given via intracameral injection during Dosing Visit 3/Day 1.

Patients will receive the following investigational product doses in the study eye on Day 1 Dosing (Visit 3) and will receive timolol maleate 0.5% ophthalmic solution to use in the non-study eye twice daily starting on the evening of Day 1 and continuing through the day prior to Month 12 (Visit 16), Month 18 (Visit 22), or Month 21 (Visit 25) for Cohort 2 or Month 24 (Visit 28) for Cohort 3.

- Cohort 2 low dose level: two implants/eye of ENV515-3 (28.2 μg/eye)
- Cohort 3 low and high dose levels:
 - one implant/eye of ENV515-3-2 (26.1 μg/eye)
 - two implants/eye of ENV515-3-2 (52.2 μg/eye)

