- 12. Assess vital signs only at Visit 16/Month 12 and Visit 19/Month 15 (can be performed anytime during the site visit)
- 13. Perform dilated funduscopic examination only at Visit 16/Month 12
- 14. Collect non-fasting blood and urine for clinical laboratory tests only at Visit 16/Month 12
- 15. Collect used timolol maleate 0.5% ophthalmic solution bottle and distribute new bottle to patient

Patients are expected to remain in the clinic for the completion of all procedures (\sim 7:30 a.m. to \sim 9:00 a.m.).

Before patients leave the clinic, they should receive an appointment for their next study visit and the instructions provided in Section 12.3.4.

12.12. Visit 22/Month 18 ± 7 Days/Treatment Period Study Exit, Cohort 2 **Extension 1 (if patient chooses not to enroll in Extension 2)**

If a patient discontinues prior to the Visit 22/Month 18, or declines to continue into the Cohort 2 Study Extension 2 the following procedures are to the performed. If the patient chooses to continue into the Cohort 2 Study Extension 2, please follow the procedures in Section 12.13.

Query patient about changes in concomitant medications and whether or not they have experienced symptoms suggesting an AE. AEs will be documented.

- 1. Assess BCVA (ETDRS) with manifest refraction
- 2. Perform pupil measurement
- 3. Perform slit lamp biomicroscopy
- 4. Perform corneal staining
- 5. Measure IOP at 8 am (±30 minutes, please make sure that timolol maleate 0.5% ophthalmic solution is administered after the IOP measurement)
- 6. Perform gonioscopy (if gonioscopy images are collected, please conduct the gonioscopy after the 4:00 p.m. IOP measurement)
- 7. Perform pachymetry (contact)
- 8. Perform specular microscopy (non-contact) for both eyes (can be performed anytime during the visit)
- 9 Assess VF
- 10. Perform anterior chamber OCT with the ENV515 implant(s) in the field of view of at least one OCT image
- 11. Measure IOP at 10:00 a.m. (±30 minutes)
- 12. Measure IOP at 4:00 p.m. (±30 minutes)
- 13. Perform dilated funduscopic exam
- 14. Perform body system assessment (can be performed anytime during the site visit)
- 15. Assess vital signs (can be performed anytime during the site visit)
- 16. Collect non-fasting blood and urine for clinical laboratory tests and systemic PK
- 17. If female of childbearing potential, perform urine pregnancy test
- 18. Collect used timolol maleate 0.5% ophthalmic solution bottle
- 19. Complete the exit form

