13.3.4. Patient Instructions

Before patients leave the clinic, they should receive an appointment for their next study visit and the following instructions:

• Remember to use timolol maleate 0.5% ophthalmic solution twice daily (as close to 8:00 a.m. and 8:00 p.m. as you can ± 60 minutes) in the non-study eye. DO NOT PUT timolol maleate 0.5% ophthalmic solution in the eye that received the ENV515 implants. Continue using timolol maleate 0.5% ophthalmic solution until one day prior to Visit 16 (Month 12 ± 7 days). Please remember to bring timolol maleate 0.5% ophthalmic solution with you at each subsequent visit so that it can be

administered after the 8:00 a.m. IOP measurement. It will need to be collected from you before issuing a new bottle at applicable visits.

- Continue to withhold (not use) all other eye drop medications until the end of the study (if appropriate). With your investigator's approval, you may be able to use artificial tear eye drops.
- Remember not to wear contact lenses.
- Please avoid physical activities associated with jarring physical motions, such as horseback riding, for the rest of the study.
- Call your study site if you have any problems.

13.4. Visit 4/Day 2 + up to 3 Days/Treatment Period, Cohort 3

Query patient about changes in concomitant medications and whether or not they have experienced symptoms suggesting an AE. AEs and concomitant medications will be documented.

Assessments will be conducted in the following order. Both eyes will be evaluated at all ophthalmic assessments unless otherwise noted:

- 1. Assess BCVA (ETDRS) with manifest refraction
- 2. Perform slit lamp biomicroscopy
- 3. Perform corneal staining
- 4. Measure IOP at 8:00 a.m. (±30 minutes) Please make sure that timolol maleate 0.5% ophthalmic solution is administered after the IOP measurement.
- 5. Perform gonioscopy
- 6. Perform pachymetry (contact)
- 7. Perform specular microscopy (non-contact) study eye only; Non-contact specular microscopy can be performed anytime during the site visit

Patients are expected to remain in the clinic for the completion of all procedures (\sim 7:30 a.m. to \sim 10:00 a.m.).

Before patients leave the clinic, they should receive an appointment for their next study visit and the instructions provided in Section 13.3.4.

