- 3. Measure IOP at 8:00 a.m. (±30 minutes) or when feasible
- 4. Perform pachymetry (contact)
- 5. Perform specular microscopy (non-contact), can be performed anytime during the site visit
- 6. Adverse Event assessment
- 7. Concomitant medication assessment

14. TREATMENT OF PATIENTS, COHORTS 2 AND 3

14.1. Treatments to be Administered, Cohorts 2 and 3

14.1.1. Implantation of ENV515, Cohorts 2 and 3

Treatment will consist of a single intracameral injection of low dose ENV515-3 (travoprost) Intracameral Implants in Cohort 2, and a single intracameral injection of low or high dose of ENV515-3-2 (travoprost) Intracameral Implants in Cohort 3 into the study eye, defined as the qualifying eye with higher mean diurnal IOP during the Baseline Visit or the left eye if both eyes have the same mean diurnal IOPs at the Baseline Visit. The study eye will be selected during the Dosing Visit (Visit 3). All investigators will be trained in implant loading, administration, and retrieval (if necessary) by Envisia. Timolol maleate 0.5% ophthalmic solution will be administered into the non-study eye once on Day 1 at 8:00 p.m. Starting on Day 2 patients will administer timolol maleate 0.5% ophthalmic solution twice a day (8 a.m. and 8 p.m. ± 60 minutes) until the night prior to Visit 16 (Month 12) in the non-study eye.

ENV515-3 and ENV515-3-2 (travoprost) Intracameral Implants will be supplied in sterile glass vials with 1 implant per vial. The sterile implant applicator will be provided in a Tyvek® pouch. The packaging will be opened and the implant applicator and the implants will be placed into a sterile field. Implants will be loaded into the implant applicator by the trained investigator or trained Envisia staff member immediately prior to dosing. Additionally, the study eye will be administered 3 doses of topical antibiotic VIGAMOX: first dose following the completion of the pre-dose assessments (Section 12.3.1 and Section 13.3.1) and immediately before and after the ENV515 implant administration as described below. The following instructions will be minimally distributed with the ENV515 implants and implant applicator:

Opening Instructions, Cohorts 2 and 3

- 1. Use sterile technique in sterile field to open primary packaging for the applicator and ENV515 implants.
- 2. Open ENV515 Implant Applicator packaging and place the sterile ENV515 applicator into sterile field.
- 3. Do not open glass vial containing implants until ready to load into the applicator.

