2.4 Treatment Regimens

Patients will receive the following investigational product doses in the study eye on Day 1 Dosing (Visit 3) and will receive timolol maleate 0.5% ophthalmic solution to use in the nonstudy eye twice daily starting on the evening of Day 1 and continuing through the day prior to Month 12 (Visit 16), Month 18 (Visit 22), or Month 21 (Visit 25) for Cohort 2 or Month 24 (Visit 28) for Cohort 3.

- Cohort 2 low dose level: two implants/eye of ENV515-3 (28.2 µg/eye)
- Cohort 3 low and high dose levels:
 - One implant/eye of ENV515-3-2 (26.1 μ g/eye)
 - Two implants/eye of ENV515-3-2 (52.2 μ g/eye)

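### Timolol instructions for Cohorts 2 and 3 still end control-eye dosing at Month 12 and make no exception for timolol rescue, and SAP Section 7 wrongly says control compliance is not collected

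*Protocol*

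**What the plan says.** **Stop date.** Three protocol sections end fellow-eye timolol at Month 12:

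- 12.3.4 (Cohort 2): "until one day prior to the last study visit, Visit 16 (Month 12 ± 7 days".
- 13.3.4 (Cohort 3): "Continue using timolol maleate 0.5% ophthalmic solution until one day prior to Visit 16 (Month 12 ± 7 days".
- 14.1.1 (both cohorts): "until the night prior to Visit 16 (Month 12) in the non-study eye".

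Other current text continues it through the extensions. Protocol Section 10 has dosing "continuing through the day prior to Month 12 (Visit 16), Month 18 (Visit 22), or Month 21 (Visit 25) for Cohort 2", and to Month 24 for Cohort 3. SAP 2.4 for Cohorts 2 and 3 agrees: "Month 21 (Visit 25) for Cohort 2 or Month 24 (Visit 28) for Cohort 3". The timolol footnotes to Tables 3, 4, 6 and 7 say "Timolol maleate 0.5% ophthalmic solution is given to the patient to continue dosing BID for the remainder of the study", and the Table 7 footnote adds "A new supply of timolol maleate 0.5% ophthalmic solution will be provided on a monthly basis through Month 23 (Visit 27".

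The extension visit sections 12.11, 12.13, 13.12 and 13.14 each end by sending the patient home with "their next study visit and the instructions provided in Section 12.3.4".

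**Rescue.** Both 12.3.4 and 13.3.4 tell the patient, in capitals, not to put timolol in the implanted eye. Section 14.1.2 restricts the supplied instructions for use to the non-study eye. Section 11.6 makes twice-daily timolol the study-eye rescue in Cohort 3 and the permanent rescue after AZOPT in Cohort 2.

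**Compliance.** SAP Section 7 for Cohorts 2 and 3 says no compliance information will be collected for the active control. Protocol 16.3 requires unopened or clearly unused bottles, or 5 or more days of non-use before a visit, to be noted in the accountability log, the patient's chart and the eCRF. Protocol 18.1.2 also says compliance will be collected.

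**The concern.** The timolol eye is the only active control in Cohorts 2 and 3. A patient who follows the take-home text literally would stop control drops at Month 12 while still attending extension visits at which that eye's pressure is read and compared with the implant eye. SAP 8.1 summarises pressure and its change from baseline by visit and eye, with no cut-off at Week 12. Fellow-eye readings from the extensions would therefore enter planned Table 14.2.1 labelled as timolol.

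A patient put on timolol rescue would hold written instructions forbidding the prescribed drop in the prescribed eye.

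The SAP statement on compliance compounds both problems. The record that would show whether control drops were being used is required by the protocol, but the analysis plan says it does not exist.

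**Working it through.** The plan states no figure on this point, so the check is a comparison of texts plus simple counts.

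**1. Where each restriction appears.** The Visit 16 stop is in all three of 12.3.4, 13.3.4 and 14.1.1. The express bar on the implant eye is in 12.3.4 and 13.3.4 only. Section 14.1.1 directs timolol to the non-study eye without prohibiting it in the other; 14.1.2 adds the non-study-eye limit on the supplied instructions.

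**2. Visits at which the outdated text is re-issued** (on or after the Visit 16 date, maximum per patient):

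- Cohort 2: Visits 16–21 (12.11) = 6, plus Visits 22–24 (12.13) = 3; total 9.
- Cohort 3: Visits 16–21 (13.12) = 6, plus Visits 23–27 (13.14) = 5; total 11.

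Sections 13.12 and 13.14 are Cohort 3 sections, but they cite 12.3.4, the Cohort 2 instructions, which describe Visit 16 as the last visit.

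**3. Intended dosing period beyond the written stop** (maximum, since the extensions are optional):

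- Cohort 2: 21 − 12 = 9 months.
- Cohort 3: 24 − 12 = 12 months.

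**4. Scheduled 8 a.m. fellow-eye readings after Month 12** (maximum per patient):

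- Cohort 2: Visits 17–25, so 25 − 17 + 1 = 9.
- Cohort 3: Visits 17–28, so 28 − 17 + 1 = 12.
- Week 2, 6 and 12 readings affected: 0. Days 14, 42 and 84 all precede Month 12.

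**5. What the same sections say about supply.** In 12.11 (step 15), 12.13 (step 11), 13.12 (step 9) and 13.14 (step 9) the site collects the used timolol bottle and gives out a new one. Each section also tells the site to see that timolol is given after the 8 a.m. reading. The visit procedures therefore assume continued dosing, while the take-home text they cite says dosing has ended.

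**6. A gap in the correct text.** For Cohort 3, Section 10 and SAP 2.4 name only Visit 28. A Cohort 3 patient may also exit at Visit 16 (13.11) or Visit 22 (13.13), so these two sections need both visits added.

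**7. Origin of the SAP statement.** Section 7 of the Cohort 2/3 SAP refers to a day of randomization, although its own Section 2.5 says there was none. The wording closely follows Section 7 of the Cohort 1 SAP and looks carried over.

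**The case against.** The strongest reply is that no site following a whole visit section would leave the control eye untreated. It hands over a fresh bottle, sees the morning drop given after the reading, and has Section 10 and the schedule footnotes stating continued dosing. In 12.3.4 one can also take the last study visit as the operative phrase, and for an extension patient that visit is later. This largely stands, and it is why the impact is low. It does not remove the conflict: 13.3.4 and 14.1.1 contain no such phrase, and 12.3.4 itself equates the last visit with Visit 16.

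On rescue, the prohibition is a default first given on dosing day. Rescue comes later, at the investigator's direction, and Table 5 gives timolol rescue its own row for Cohort 3. An investigator starting it would have to say which eye to treat. This also stands as mitigation. The written text is nevertheless repeated afterwards without an exception.

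A reader might go further and infer that:

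- **The fellow eye goes untreated for 43% (9/21) of follow-up in Cohort 2 and 50% (12/24) in Cohort 3.** These are calendar shares after the written stop date. The re-supply steps argue against reading them as lost dosing.
- **A rescued implant eye would be denied timolol.** Section 11.6 and Table 5 provide for giving it.
- **14.1.1 also bars timolol from the implant eye.** It does not.
- **The IOP comparison is biased by some amount.** Nothing in the documents supports an mmHg figure.

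**Conclusion.** The point holds as a low-impact inconsistency in operative patient instructions, together with one incorrect SAP statement. It is not a flaw in the statistical design.

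The ceilings are 9 months past the written stop in Cohort 2 and 12 in Cohort 3, with 9 and 12 scheduled 8 a.m. fellow-eye readings per patient in those periods. They assume a patient who takes every optional extension. The analytic reach is small: Cohort 2 extension pressure measures are exploratory, the Cohort 3 extension synopses list only safety measures, and the SAP plans no formal testing.

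The protocol edits help only patients still under follow-up. The documents do not settle how many that is: Section 1.2 calls Cohort 2 both ongoing and completed, and the January 2019 SAP says the IND is being withdrawn. The SAP correction bears on the abbreviated study report in either case.

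**What to change.** - **Stop date:** in 12.3.4, 13.3.4 and 14.1.1, replace Visit 16 with the patient's own exit visit (16, 22 or 25 in Cohort 2; 16, 22 or 28 in Cohort 3). List Visits 16 and 22 for Cohort 3 in Section 10 and SAP 2.4.
- **Rescue:** after the prohibition in 12.3.4 and 13.3.4, add 'unless your study doctor has prescribed timolol as rescue for that eye', with a matching exception in 14.1.2.
- **Cross-references:** point 13.12 and 13.14 to 13.3.4.
- **SAP Section 7 (Cohorts 2 and 3):** replace the sentence on control compliance with a statement that timolol non-use noted in the eCRF under protocol 16.3 will be listed by patient and visit, for example in exposure listing 16.4.5. SAP 9.2 limits calculated exposure to the study eye, so the entry should be labelled as a fellow-eye record.

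The cost is wording in five protocol sections, two cross-references, SAP 2.4, one sentence in SAP Section 7 and an added entry in a listing already planned. No new visits, measurements or tables are needed.
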